6.3 ON STUDY MONITORING, DAY 1 OF h-ATG THROUGH HOSPITAL DISCHARGE

Abbreviated Title: Early Initiation of Oral Therapy for Naïve Severe Aplastic Anemia (SAA)

Version Date: 11/05/2025

On treatment monitoring will consist of the following, unless the hospitalization is interrupted due to the participant leaving the hospital “on pass” but not to exceed more than 7 days:

- Pregnancy test (urine or blood HCG in women of childbearing potential) does not need to be repeated if done within two weeks of initiation of h-ATG unless clinically indicated
- CBC with differential (daily)*
- Acute care, Mineral, and Hepatic (every other day)*
- Reticulocyte count (weekly +/- 3 days)*
- Vital signs (daily)
- CsA blood level will be monitored every week (+/- 3 days) while inpatient in the hospital and continued per section 6.4. The blood level will be monitored to ensure therapeutic range of 200 – 400 ng/ml is achieved. CsA dosage will be adjusted to target this range unless otherwise indicated by PI due to toxicities or intolerance. More frequent drug serum levels may be obtained as needed to achieve target therapeutic levels and avoid toxicity.

*In case of prolonged hospitalization (beyond 14 days), the marked labs will be required no more than twice a week.

6.4 ON STUDY MONITORING (HOSPITAL DISCHARGE THROUGH 6 MONTHS)

After completing h-ATG administration, subjects will remain hospitalized until clinically stable. Post-discharge, subjects may be followed by their home physician or at the Clinical Center. Progress notes and laboratory results from home physicians will be faxed to the research nurse. Standard of care tests will be done as needed and may include the tests listed below. Changes in frequency of the tests below will be performed as clinically indicated at the investigator’s discretion.

- Complete blood counts with differential every 1-2 weeks (+/- 4 days). Only the following parameters will be recorded in the clinical database because of their relevance to the underlying disease and study treatment: absolute lymphocyte count (ALC) or lymphocyte percentage, absolute neutrophil count (ANC), or neutrophil percentage and white blood cell count if an absolute neutrophil count is not provided, hemoglobin, platelets, and absolute reticulocyte count (or reticulocyte percentage and red blood cells [RBC] if an absolute reticulocyte count is not provided).
- Hepatic and renal panels (home panels must include hepatic transaminases, urea nitrogen (BUN), serum creatinine, and total bilirubin) every 1-2 weeks (+/- 4 days). Magnesium may be requested in patients with hypomagnesemia per PI.

Only the following parameters will be recorded in the clinical database because of their relevance to the underlying disease and study treatment: aspartate aminotransferase (AST), alanine aminotransferase (ALT), alkaline phosphatase (ALP), total bilirubin, creatinine, blood urea nitrogen (BUN), glucose, sodium, potassium, CO₂ and chloride. Direct bilirubin will be obtained per PI discretion if total bilirubin is elevated.

- CsA blood levels will be monitored every week (+/- 3 days) for the first month and then every 2 weeks (+/- 4 days) for the remainder of the treatment period once levels are stabilized in the therapeutic range of 200 – 400 ng/ml. CsA dosage will be adjusted to

target this range unless participants cannot tolerate therapeutic dosing of CsA. More frequent drug serum levels may be obtained as needed to achieve target therapeutic levels and avoid toxicity, and conversely less frequent levels may be obtained as needed in individuals unable to tolerate therapeutic dosing of CsA. The dose may not necessarily be adjusted following every out of range CsA level; the decision to adjust the dose will be determined by the clinician judgement based on multiple data sources, that could include but not limited to time of measurement, prior trend of CsA levels, estimation of steady state, concomitant medications that may affect CsA metabolism, and renal function. CsA monitoring will be discontinued at 6 months.

Landmark 1, 2, 3 and 6-month monitoring

Subjects must be evaluated at the NIH Clinical Center at the 6-month (+/-10 days) time point. 1 and 2-month (+/- 10 days) landmark time points are for evaluation of early hematological response only; therefore, do not require a visit at the Clinical Center. Per PI discretion, the 3 month time point visit may be conducted with subjects' local physician during special circumstances, where the risk of evaluation at the CC may outweigh the benefit. Tests with * below can be omitted from 3 month evaluation if the visit is being conducted with home physician. In addition, a tele/video meeting with the patient will be conducted by the bone marrow failure team member.

1- and 2-month

- Complete blood counts with differential
- Reticulocyte count

3- month and 6- month

- History and physical examination
- Complete blood counts with differential
- Acute care (Na, K, Cl, CO₂, creatinine, glucose, and urea nitrogen), Mineral (Phosphorus, Magnesium, Albumin, and Calcium), Hepatic (Alk Phosphatase, ALT, AST, Total Bilirubin), and Other (Total Protein, Uric Acid, and LDH). Direct bilirubin will be obtained per PI discretion if total bilirubin is elevated.
- Reticulocyte count and other (cyclosporine level, ferritin, iron, transferrin, lactate dehydrogenase, protein)
- Urine pregnancy test (woman of childbearing age only)
- Bone marrow aspiration and core biopsy, to be stained for standard morphologic analysis and quantitation of cellularity with hematoxylin and eosin, and special stains to assess reticulin and collagen, primitive stem and progenitor cells via CD34 immunohistochemistry, and other lineage-specific or special stains as indicated to classify any abnormalities**
- Bone marrow chromosomal analysis via standard cytogenetic techniques**
- Flow cytometry of the peripheral blood to quantitate GPI-negative cells
- Lymphocyte peripheral blood phenotyping (analysis of T, B, and NK subsets via flow cytometry)*
- EKG will be performed at 3 months
- Transfusion records to be obtained including number of transfusions since last landmark visit as well as date of last transfusion

Abbreviated Title: Early Initiation of Oral Therapy for Naïve Severe Aplastic Anemia (SAA)

Version Date: 11/05/2025

** At each of these visits, up to 30 mL total including the sample for research may be collected. Bone marrow aspiration, biopsy, and chromosomal analysis may be omitted if one was performed within 4 weeks of the timepoint analysis.

6.5 LONG TERM FOLLOW UP (6 MONTHS TO 5 YEARS)

After the 6-month visit, subjects must be evaluated at the Clinical Center at 12 months (+/- 30 days) and then yearly thereafter to 5 years (+/- 90 days) except in special circumstances (see below). Subjects will be seen by their home physician as clinically indicated and the Hematology Branch investigators and home physicians will remain in communication. Home physicians will monitor blood counts and other clinical parameters as clinically indicated. The following tests will be performed at each Clinical Center visit. At the clinical investigator's discretion, participants may be evaluated more frequently if medically indicated based on disease status.

PI discretion, during special circumstances (such as COVID 19 outbreak) where the risk of evaluation at the CC may outweigh the benefit, a tele/video visit may be conducted and test results received from subjects' local physician may be used. Tests with * below can also be omitted.

- History and physical examination
- Complete blood counts with differential
- Acute care (Na, K, Cl, CO₂, creatinine, glucose, and urea nitrogen), Mineral (Phosphorus, Magnesium, Albumin, and Calcium), Hepatic (Alk Phosphatase, ALT, AST, Total Bilirubin), and Other (Total Protein, Uric Acid, and LDH). Direct bilirubin will be obtained per PI discretion if total bilirubin is elevated
- Reticulocyte count and other (ferritin, iron, transferrin, lactate dehydrogenase, protein)
- Urine pregnancy test (woman of childbearing age only)
- Bone marrow aspiration and core biopsy, to be stained for standard morphologic analysis and quantitation of cellularity with hematoxylin and eosin, and special stains to assess reticulin and collagen, primitive stem and progenitor cells via CD34 immunohistochemistry, and other lineage-specific or special stains as indicated to classify any abnormalities (optional for year 3, 4 and 5 depending on the peripheral blood counts and concern for clonal evolution)*
- Bone marrow chromosomal analysis via standard cytogenetic techniques (optional for year 3, 4 and 5 depending on the peripheral blood counts and concern for clonal evolution)*
- Flow cytometry of the peripheral blood to quantitate GPI-negative cells
- Lymphocyte peripheral blood phenotyping (analysis of T, B, and NK subsets via flow cytometry)
- Date of last transfusions (both blood and platelets) to be recorded in database since landmark visit

*At these visits, up to 30 mL total including the 15ml for exploratory/correlative research sample may be collected. For minors, the bone marrow biopsy & aspirate procedure will be done with general anesthesia.

6.6 GENETIC AND OTHER TESTS (MAY BE PERFORMED IN SOME PATIENTS)

- Testing for acquired somatic mutations in genes linked to leukemia and bone marrow

failure in a CLIA-certified commercial, and flow cytometry may be performed.

- Presence of mutations in genes known to be associated with inherited bone marrow failure disorders and/or telomere length in a CLIA-certified laboratory. When novel mutations are found, the respective samples may be further evaluated.
- Diepoxybutane stimulation testing of peripheral blood may be performed in subjects with cytopenias under the age of 40 or if clinical history or characteristics suggest Fanconi anemia.

6.7 RETURN OF RESEARCH RESULTS

For tests performed at the Clinical Center, if there are not expected (incidental) research test results relevant to subjects' disease (SAA) and can put them at high risk of other disease, we will provide subjects with the test results and the appropriate follow-up information.

6.8 EXTENDED ACCESS FOR RELAPSE

Indicated below are the procedures that can be performed on subjects that re-start oral drugs (cyclosporine, eltrombopag or both) due to relapse. At the clinical investigator's discretion, participants may be evaluated as medically indicated based on disease status. The procedures may be performed by the subjects' home physician or at the Clinical Center. If testing is done by home physician, progress notes and laboratory results from home physician will be sent to the research team. Subjects will be seen at the Clinical Center as clinically indicated while on extended access for relapse, but no less than annually until 5 years. Below is the list of procedures that may be performed at the clinical center visit at least once per year (+/- 90 days) or more frequently as medically indicated.

Procedures that may be performed when drugs are re-started:

- History and physical examination
- Pregnancy test (urine or blood HCG in women of childbearing potential) – Optional
- Complete blood counts with differential
- Reticulocyte count
- Chemistry panel (NIH Acute care, Mineral, Hepatic and Other panel, home laboratory chemistry panel must include electrolytes, hepatic transaminases, urea nitrogen (BUN), serum creatinine, total bilirubin, and reticulocyte count)
- CsA blood level will be monitored until levels are stabilized in the therapeutic range of 200 – 400 ng/ml. CsA dosage will be adjusted to target this range. More frequent drug serum levels may be obtained as needed to achieve target therapeutic levels and avoid toxicity. This test is only required if patient is on therapeutic levels of cyclosporine.
- Bone marrow aspiration and core biopsy, to be stained for standard morphologic analysis and quantitation of cellularity with hematoxylin and eosin, and special stains to assess reticulin and collagen, primitive stem and progenitor cells via CD34 immunohistochemistry, and other lineage-specific or special stains as indicated to classify any abnormalities (optional for year 3,4, and 5 based on the peripheral blood counts and concern for clonal evolution)*
- Bone marrow chromosomal analysis via standard cytogenetic techniques (optional for year 3,4, and 5 based on the peripheral blood counts and concern for clonal evolution)*
- Flow cytometry of the peripheral blood to quantitate GPI-negative cells

Abbreviated Title: Early Initiation of Oral Therapy for Naïve Severe Aplastic Anemia (SAA)

Version Date: 11/05/2025

- Lymphocyte peripheral blood phenotyping (analysis of T, B, and NK subsets via flow cytometry)

*At these visits, up to 30 mL total including the 15ml for exploratory/correlative research sample may be collected. For minors, the bone marrow biopsy & aspirate procedure will be done with general anesthesia.

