day /month				D 1	D 2	D 3	D 4		M1	M2	M3	M6	M12	M24	M36	M48	M60
Female, Pregnancy Test (blood or urine)	x ¹		x						x	x	x	x	x	x	x	x	x ^{3/C}
Acute care/mineral panels	x ³	x ³	x		x	x			x	x	x	x	x	x	x	x	x ³
Hepatic Panel	x ³	x ³	x		x	x			x	x	x	x	x	x	x	x	x ³
LDH panel	x ³		x		x	x			x	x	x	x	x	x	x	x	x ³
Total Protein, uric acid, CK			x														
Thyroid Function Test			x														
Folate Level, B12 Level			x														
Iron Panel (ferritin, transferrin, % saturation)			x						x	x	x	x	x	x	x	x	
HEMATOLOGY LABS																	
CBC with differential	x ³	x ³	x	x	x	x	x	x ³	x ³	x	x	x	x	x	x	x	x ³
Reticulocyte Count	x ³	x ³	x					x ³	x ³	x	x	x	x	x	x	x	x ³

Abbreviated Title: Early Initiation of Oral Therapy for Naïve Severe Aplastic Anemia (SAA)

Version Date: 11/05/2025

EVALUATION AND ASSESSMENTS	Screening /Baseline	Off Site Monitoring	1 st Visit at Clinical Center	On Site Monitoring				Follow Up Visit									Relapse
				5	6	7	8	11	12	13	14	15	16	17	18	19	
PROTOCOL TIMEPOINT	1	2	3														20
Window +/- days	* +/- 4 weeks	+/- 8 Weeks	* +/- 8 Weeks					+/- 10D	+/- 10D	+/- 10D	+/- 10D	+/- 30D	+/- 90D	+/- 90D	+/- 90D	+/- 90D	
day /month				D 1	D 2	D 3	D 4		M1	M2	M3	M6	M12	M24	M36	M48	M60
Direct Antiglobulin Screen			x														
Type and Screen	x ³		x														
Viral Serologies																	
Hepatitis A, B, C			x														
HIV			x														
HSV			x														
EBV and CMV			x														
Other Blood & Bone Marrow Tests																	
Lymphocyte phenotyping T, B, NK			x						x	x	x	x	x	x	x	x ³	
Telomere length of leukocytes			x														
Flow Cytometry of peripheral blood			x						x	x	x	x	x	x	x	x ³	
HLA typing			x														
Cyclosporine Level			x														x ³

Abbreviated Title: Early Initiation of Oral Therapy for Naïve Severe Aplastic Anemia (SAA)

Version Date: 11/05/2025

EVALUATION AND ASSESSMENTS	Screening /Baseline	Off Site Monitoring	1 st Visit at Clinical Center	On Site Monitoring				Follow Up Visit									Relapse
				5	6	7	8	11	12	13	14	15	16	17	18	19	
PROTOCOL TIMEPOINT	1	2	3														20
Window +/- days	* +/- 4 weeks	+/- 8 Weeks	* +/- 8 Weeks					+/- 10D	+/- 10D	+/- 10D	+/- 10D	+/- 30D	+/- 90D	+/- 90D	+/- 90D	+/- 90D	
day /month				D 1	D 2	D 3	D 4		M1	M2	M3	M6	M12	M24	M36	M48	M60
Bone Marrow aspiration and core biopsy for standard morphologic analysis	x ⁸		x									x	x	x	x	C	C
Bone Marrow for chromosomal analysis			x									x*	x*	x	x	C	C
Telephone Weekly Follow Up (+/- 3 days) Appendix B																	

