x ⁵ = dose is 2mg/kg/day																		
x ⁶ = dose increase based on age, section 5.1																		
x ⁷ = responders will have dose decrease, 2 mg/kg/day																		
x ⁸ = drug discontinued																		
X ⁹ =outside bone marrow results accepted after verification at the NIH																		
X* = Bone marrow aspiration, biopsy, and chromosomal analysis may be omitted if one was performed within 4 weeks of the timepoint analysis.																		
C = Considered optional																		

Abbreviated Title: Early Initiation of Oral Therapy for Naïve Severe Aplastic Anemia (SAA)

Version Date: 11/05/2025

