- Initiation of additional immunosuppressive therapy other than steroids or cyclosporine (if beyond 6 months then mycophenolate mofetil can also be administered per PI discretion in patients who cannot tolerate cyclosporine and who require immunosuppression) or if beyond 2 years, enroll in other available clinical trials.

Pregnancy: This protocol does not enroll patients who are pregnant or women of child-bearing potential unless they are using contraception during the study treatment period (Section 4.3).

Because aplastic anemia is a disease of young adults, if a woman becomes pregnant while participating in the study despite stringent contraception requirements and education by the study team regarding the risks of relapsed aplastic anemia with pregnancy upon study entry and at

Abbreviated Title: Early Initiation of Oral Therapy for Naïve Severe Aplastic Anemia (SAA)

Version Date: 11/05/2025

every landmark visit, patient may remain on study. This limited inclusion of pregnant women on this study permits capture of the secondary endpoint (relapse of aplastic anemia) without exposing the subject/fetus/neonate to study drugs or invasive protocol procedures.

- If a patient becomes pregnant while on study drugs (CSA and/or EPAG), patient will discontinue the medications immediately but may remain on study
- If a patient becomes pregnant during follow-up period and not on any study treatments, patient may remain on study
- No investigational interventions or research procedures will be performed during pregnancy (if landmark visit is due during pregnancy, it will be delayed till after). All clinical decisions about pregnancy management will be made by the patient and the treating physician.
- If a patient relapses with aplastic anemia during pregnancy, no treatment will be provided on study; recommendations will be provided to the local treating physician for clinical management and if pursued any treatment other than supportive care (transfusions), patient will be taken off study
- Blood count monitoring with complete blood counts (CBCs) will be obtained with increased frequency than otherwise indicated, especially in later gestation, to monitor for AA relapse
- Fetus/neonate is not a research subject in this protocol
- No inducements, monetary, or otherwise, will be offered to terminate a pregnancy
- Individuals engaged in the research will have no part in any decisions as to the timing, method, or procedures used to terminate a pregnancy.

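### Section 6.8 leaves the pregnancy test optional when cyclosporine or eltrombopag is restarted for relapse, so after a drug-free period pregnancy status need not be known at restart

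*Combined protocol and SAP*

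**What the plan says.** Section 6.8 covers participants who go back on cyclosporine, eltrombopag or both because of relapse. Its list is headed "Procedures that may be performed when drugs are re-started", and the pregnancy entry is downgraded once more: "Pregnancy test (urine or blood HCG in women of childbearing potential) – Optional". The work may be done by the home physician or at the Clinical Center.

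Section 9.6 sets the rules for pregnancy. A woman who conceives while off study drug may stay enrolled. A woman who conceives on study drug stops it at once. For relapse it states: "If a patient relapses with aplastic anemia during pregnancy, no treatment will be provided on study". Pregnant women are kept in follow-up so that relapse can be observed "without exposing the subject/fetus/neonate to study drugs or invasive protocol procedures".

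The other controls are:
- Section 4.2, exclusion 21: pregnancy at screening or before the first dose excludes.
- Section 4.2, exclusion 20: contraception is required while study treatment is being dosed.
- Section 6.3: the test before h-ATG may be no more than two weeks old.
- Sections 6.4 and 6.5: a test at months 3, 6 and 12 and at each yearly visit.
- Sections 5.4.4 and 10.7.5: drug is stopped once pregnancy is known.

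Under Section 5.1, responders take reduced-dose cyclosporine through month 24.

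**The concern.** The rule in Section 9.6 needs a known pregnancy in order to work, and Section 6.8 does not make sure that the pregnancy is known. A site that follows Section 6.8 to the letter can restart either drug in a woman whose pregnancy has not been recognized. Section 9.6 then comes into play only after the fetus has been exposed.

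The protocol itself treats relapse and pregnancy as linked. Section 2.1 names pregnancy among the conditions associated with aplastic anemia. Section 9.6 has women educated at entry and at every landmark visit "regarding the risks of relapsed aplastic anemia with pregnancy", and asks for more frequent blood counts in pregnancy to detect relapse. Section 4.3 describes the fetal risk of eltrombopag as unknown. What is at stake is the safety of a participant and her fetus, not the trial's inference.

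**Working it through.** The plan states no figure here to reproduce. The check is a comparison of provisions with a little arithmetic.

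**1. Does any section require a test at restart?** Exclusion 21 is confined to screening and Day 1. Section 6.3 is confined to h-ATG. Sections 6.4 and 6.5 follow the visit calendar and not drug starts. Sections 5.4.4, 9.6 and 10.7.5 respond to a pregnancy already found. Section 6.8 is the only one that addresses restart, and there the test is optional. So none does.

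**2. How old may the last required test be when drug is started?**
- h-ATG (Section 6.3): 14 days.
- First oral dose, loosest reading: outside results up to 30 days before enrollment (Section 6.1), plus up to 4 weeks from eligibility to treatment (Section 4): 30 + 28 = 58 days. Section 12.5 has drug shipped within 24 to 48 hours of consent, so about 30 days plus delivery is more realistic.
- Restart between yearly visits after month 24: no limit is set. Nominally the last test is up to 365 days old. With the ±90-day windows of Section 6.5 the extreme is 365 + 90 + 90 = 545 days, but only if two successive visits fall at opposite limits.

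**3. When does the gap matter?** For a responder who stops cyclosporine at month 24, 60 − 24 = 36 months of follow-up are drug-free unless relapse occurs. The contraception condition does not clearly reach that period. Before month 24 the gap is narrower. Under Sections 5.1 and 7, relapse is then usually met by a higher dose of cyclosporine already being taken, and a woman who resumes eltrombopag is normally still on cyclosporine and still under the contraception condition.

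**4. Does the Schedule of Events agree?** Probably. The last cell of the row "Female, Pregnancy Test (blood or urine") reads x with superscript 3/C, and the key says "C = Considered optional". Several features suggest that the last cell is the Relapse column: the column header ends there, both oral drugs reappear there after being marked discontinued, and the cyclosporine-level row is filled there although Section 6.4 says "CsA monitoring will be discontinued at 6 months". But the machine-read table is shifted. Counted the same way, its day/month row puts M60 in that same last cell. The table is consistent with Section 6.8 but is not independent proof.

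**5. How many tests would a requirement add?** The assumptions are 80 patients, 83% response (Section 2.3.7), 40% cumulative relapse (Section 2.3.5), independence, and every relapse counted as one restart.
- Women 16/36 (Table 1 of Section 2.3.7): 80 × 16/36 × 0.83 × 0.40 = 11.8.
- Women 52% (Section 12.1): 80 × 0.52 × 0.83 × 0.40 = 13.8.

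That is roughly 10 to 15 tests. Repeat restarts would add to this. Women not of childbearing potential, and relapses met only by a dose increase, would reduce it. If 14% relapse by 2 years (Section 2.3.3), the share after month 24 is 0.40 − 0.14 = 0.26, giving 7.7 to 9.0. The two relapse rates may come from different cohorts and follow-up, so this split is weak.

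**The case against.** The strongest reply is that Section 6.8 leaves room for judgment and contradicts nothing. Every restart procedure in it is permissive, blood counts and chemistry included, and the investigator may order the test. Section 9.6 says what to do in pregnancy; it sets no testing schedule. This stands: the two sections do not conflict in words. The gap lies in what following both of them allows.

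The second reply is that other safeguards exist. The yearly urine test in Section 6.5 is not among the tests that may be omitted in special circumstances. Women are educated at each landmark visit. Section 10.7.5 has pregnancy information collected in post-treatment follow-up as well. The restart list opens with history and examination, and the second relapse criterion in Section 7 asks whether another clinical process explains the decline. These lower the risk, but none establishes current status when drug restarts.

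The third reply is that the hazard should not be inflated. Section 12.3.3 gives Category C, with embryolethality and lower fetal weight at maternally toxic doses in animals, no major structural malformations in rats and no fetotoxicity or teratogenicity in rabbits. Section 12.3.2 states no fetal risk for cyclosporine, although Section 9.6 stops it in pregnancy. This also stands. The case rests on the plan's own aim of avoiding fetal exposure and does not depend on demonstrated harm.

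**Conclusion.** The point holds as a modest participant-safety gap that is worth closing. Section 6.8 is the firm evidence: the test is optional at restart, and no other provision supplies it. After a drug-free period, chiefly beyond month 24, the last required test may nominally be up to a year old.

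Three stronger readings are tempting but unsupported. A reader might infer that the plan allows a woman known to be pregnant to be re-treated on study; Section 9.6 rules that out. A reader might take the Schedule of Events as a second, independent confirmation; the table as read is too inconsistent for that. A reader might infer that many pregnancies would be exposed; the documents give no pregnancy rate, the number is probably small, and no estimate is offered.

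The conclusion assumes that sites follow Section 6.8 as written. If investigators already test at every restart, the requirement only records existing practice.

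**What to change.** In Section 6.8, take the pregnancy test out of the permissive list and make it a condition of restart: *in women of childbearing potential, a negative urine or blood hCG is required within 2 weeks before eltrombopag or cyclosporine is restarted after a period off that drug; home-physician results are accepted; if positive, the pregnancy rules of Section 9.6 apply.* Align the Relapse cell of the pregnancy row in the Schedule of Events by dropping the optional mark and keeping the acceptance of outside results. A dose increase in a woman already taking cyclosporine can stay at the investigator's discretion.

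The two-week window is the one already used before h-ATG. The cost is a small text change, one schedule cell, one inexpensive test per restart and possibly a short wait for the result.
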